Developing adaptive interventions for cocaine cessation and relapse prevention; Using event-related potentials to predict treatment outcomes in cocaine use disorder (“Adaptive trial”)

NCT02896712

Version Date: 06/15/2020

Protocol Title:	Developing adaptive interventions for cocaine cessation and relapse prevention; Using event-related potentials to predict treatment outcomes in cocaine use disorder ("Adaptive trial")
Principal Investigator:	[name]
Co-Investigators:	[name], [name], [name], [name], [name], [name], [name], [name]
Study Coordinator:	[name]
Population:	N = 160 adults (18-60 years old) with cocaine use disorder recruited from the Houston metropolitan area
Number of Sites:	Single site
Study Duration:	Four years
Study Duration per subject:	14 weeks, with 3 visits per week for a total of 42 study visits

Project Summary

Drug addiction is a chronic, devastating, but *treatable* disorder, for which there exists a growing armamentarium of evidence-based interventions, including pharmacotherapies and psychotherapies. A core principle of drug addiction treatment, however, states that *no single treatment is appropriate for everyone*; rather, treatments need to be adjusted based on patient characteristics and response in order to be maximally effective. Ideally, clinicians would identify a sequence of interventions that works best across different stages of addiction treatment, from abstinence initiation to relapse prevention. Adaptive treatment interventions have been used successfully to inform this sequential clinical decision-making process. For cocaine use disorders (CUD), the most potent intervention currently available for initiating abstinence is behavior therapy using contingency management (CM) procedures. Intensive CM has been shown to produce initial cocaine abstinence rates of 40%, unmatched by all other forms of behavioral or pharmacological treatment, making it a prototypical first-line therapy for CUD. Importantly, achievement of initial abstinence predicts future abstinence. For the clinician, these research findings translate into a straightforward question: *Can we drive CM response rates even higher with targeted adjunctive interventions?*

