The proposed sequential, multiple assignment, randomized trial (SMART) will provide the data needed to answer this question. First, we will determine whether Acceptance and Commitment Therapy (ACT) in combination with CM increases initial treatment response rates. We hypothesize that four weeks of treatment with ACT+CM will produce higher abstinence rates than initial treatment combining standard Drug Counseling with CM (DC+CM). The hypothesized synergism of ACT+CM on primary treatment mechanisms of experiential avoidance and reward sensitivity, respectively, will be examined. Second, for patients who do not respond to initial treatment, we will examine whether dopamine-targeted pharmacotherapy is an effective augmentation strategy. Specifically, we hypothesize that continued ACT+CM treatment with modafinil augmentation will be most effective in promoting abstinence relative to treatment combinations involving continued DC and/or placebo. Third, for patients who respond to initial treatment, we will assess the relative benefit of continued treatment with ACT+CM, as compared to DC+CM, to prevent relapse. ACT emphasizes goal-directed actions based

on values that are intrinsically motivating, and is thereby expected to be a more effective intervention for extending the duration of abstinence following initial treatment with intensive CM.

In summary, results from this Stage II (PA-13-078) project should support a Go/No Go decision about further Phase III, confirmatory studies. The primary aims of this project address an important NIDA research priority and have the potential to significantly impact how we tailor treatment of CUD to maximize outcomes.

Background Information

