based treatment in the community for patients actively using cocaine. DC educates patients about important concepts in addiction recovery based on the underlying philosophy that physical, emotional, spiritual, and interpersonal needs must all be addressed to support recovery. Accordingly, the DC manual covers the core topics listed in **Table B.3.2.vi**. Masters-level therapists with DC experience from our previous trials^{41, 42} will be trained and supervised by [name] (Co-I).

Contingency Management (CM). We will use the same high-magnitude CM schedule shown previously to be feasible and effective in facilitating initial cocaine abstinence.¹² Subjects will earn vouchers for cocaine-negative urine samples collected at scheduled clinic visits (MWF) each week. Under an escalating reinforcement schedule, voucher values will begin at \$15 and increase by \$10 for each consecutive negative urine. Provision of a cocaine-positive urine or failure to provide a scheduled sample will result in no vouchers earned and will reset the schedule to the initial value (\$15). Bonus vouchers (\$10) will be given for completing all study-related tasks in a given week. Subjects will redeem their earned vouchers for cash loaded to the ClinCard, a reloadable debit card.

Initial response and re-randomization. Following Phase 1 treatment, the primary outcome of response/non-response will be determined. Subjects who submit 6 consecutive (2 weeks) cocaine negative urine samples by week 4 will be classified as responders. Those who fail to meet response criteria will be classified as non-responders.

During second (Phase 2) treatment:

- Responders will continue to receive their assigned initial treatment, as described below.
- Non-responders in each initial treatment arm will be re-randomized to a second treatment consisting of pharmacotherapy augmentation with either modafinil or placebo.

All subjects will attend three clinic visits per week (MWF) during the 8 week second treatment period.

Table B.3.2.vi. 10 Core Topics for ACT and DC

Second (Phase 2) treatments	ACT	DC
Continued ACT or DC. Twice weekly 1-hour ACT and DC sessions will continue during the 8 weeks of second treatment, covering the core topics shown in Table B.3.2.vi.	Preparing to begin	Planning my recovery
	Values	Stages of recovery
	Making contact with the cost of using	People, places, things
	Creative hopelessness	Self-help groups & support systems
	Control v Willingness	Establishing a support system

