Suicide ideation and behavior assessment. The Columbia-Suicide Severity Rating Scale (C-SSRS: <http://www.cssrs.columbia.edu>) will be used to assess suicidal ideation and behavior occurrence. The C-SSRS involves a series of probing questions asked in the patient interview, integrated with information from other sources, to classify suicidal ideation and behavior into 11 preferred categories. The full assessment will be conducted at the initial intake evaluation for screening and eligibility determination. The initial screening questions will be completed at every study visit for every patient by the trained study nurse. The study site has physicians (Co-I: [name]), psychiatrists, and licensed clinical psychologist (Investigators: [name], [name], [name], [name]) on site with extensive experience in managing suicidal ideation and behavior according to established protocols in our outpatient treatment research clinic.

Analysis Plan

Bayesian framework. The Bayesian approach addresses the following study questions: 1) What is the probability that ACT+CM confers benefit relative to DC+CM on abstinence at end of first treatment; what is the best estimate of this effect and what is its precision? 2) Among non-responders at end of first treatment, what are the relative probabilities that pharmacotherapy augmentation confers benefit at end of second treatment for those initially receiving ACT+CM versus DC+CM; what are the best estimates of these effects and what is their precision? 3) Among responders at end of first treatment, what is the probability that continued ACT+CM confers benefit relative to continued DC+CM at end of second treatment; what are the best estimates of these effects and what is their precision? By estimating the probability that such effects exists, we are assessing the probability that the alternative hypothesis is true, a probability that is, by definition, not accessible to Frequentist methods. The FDA has discussed the use of Bayesian statistical methods to make decisions regarding the efficacy of new treatments as an alternative to Frequentist methods in developing clinical applications.⁷⁵⁻⁸⁰ The current proposal will provide the best, unbiased estimates for the benefit conferred across treatment sequences, conditional upon initial response, while also estimating the probability that such effects

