Hyp. 1.a. The benefit of ACT+CM over DC+CM on initial response (abstinence) rates will be greater in the subgroup of individuals with higher pretreatment EA scores. Adding the interaction term (EA-by treatment) to the logistic regression model will evaluate the moderating effect of EA.

Hyp. 1.b. ACT+CM effects on initial treatment response will be mediated by the primary hypothesized treatment mechanisms, EA and reward sensitivity. In the context of the direct effect of treatment on response, mediational modeling will evaluate the *indirect* effect of treatment on response via EA and reward sensitivity variables, using the product moment method with bootstrapped 95% CI and Bayesian posterior distributions.

Hyp. 2. For initial non-responders, continued ACT+CM treatment with pharmacotherapy (modafinil) augmentation will be most effective in promoting abstinence relative to treatment combinations involving DC and/or placebo. Logistic regression will evaluate cocaine abstinence at the end of second treatment in a set of contrasts: (1) modafinil versus placebo within each initial treatment; (2) the sequence of ACT+CM with modafinil augmentation versus DC+CM with modafinil augmentation.

Hyp. 3. For initial responders, continued ACT+CM will be more effective (higher abstinence rates; < 46% relapse rate) than continued DC+CM. Logistic regression will evaluate cocaine abstinence/relapse at end of second treatment as a function of initial treatment (ACT+CM vs DC+CM).

Power. Power estimates for Hypotheses 1, 2 and 3 will use as the primary outcome (i.e., “response”), two consecutive weeks of cocaine abstinence (BE ≤ 150 ng/mL). Initial treatment response (abstinence) rates are expected to be $\sim 40\%$, based on our previous study¹² and pooled data across cocaine clinical trials⁸⁵; however we predict a difference in response rates, favoring ACT+CM over DC+CM by about 20%, constituting a clinically meaningful treatment effect. Among initial non responders, we expect at least a

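### Hyp. 2 lists neither an overall modafinil effect nor a contrast of the two within-arm modafinil effects; comparing the arms by their probabilities of benefit does not show whether the effects differ.

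*Combined protocol and SAP*

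**What the plan says.** The Project Summary poses an overall question for non-responders: "we will examine whether dopamine-targeted pharmacotherapy is an effective augmentation strategy". It then narrows to the hypothesis that continued ACT+CM with modafinil will do best.

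The design supports both questions. Under Initial response and re-randomization: "Non-responders in each initial treatment arm will be re-randomized to a second treatment consisting of pharmacotherapy augmentation with either modafinil or placebo".

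Three parts of the Analysis Plan bear on how modafinil is judged:

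- Bayesian framework, question 2, asks "what are the relative probabilities that pharmacotherapy augmentation confers benefit at end of second treatment for those initially receiving ACT+CM versus DC+CM". The same sentence goes on to ask for best estimates of these effects and their precision. How the two probabilities are to be related is not defined.
- Analytic strategy gives one augmentation code: 1 for non-responders receiving augmentation, 0 for everyone else. No product with initial treatment is stated.
- Hypothesis testing, Hyp. 2, lists "1) modafinil versus placebo within each initial treatment; (2) the sequence of ACT+CM with modafinil augmentation versus DC+CM with modafinil augmentation". Table B.3.2.x has three Aim 2 rows: 5 vs 6, 7 vs 8 and 6 vs 8.

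The Summary under Power treats a posterior probability of benefit above 0.80 as enough for a Go decision.

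**The concern.** Each listed contrast answers a narrower or different question. The within-arm contrasts ("1) modafinil versus placebo within each initial treatment") each use only part of the re-randomised patients. The sequence contrast compares two groups that both take modafinil, so it carries the ACT versus DC difference together with any difference in drug effect. Neither one asks whether modafinil helps non-responders overall, or whether it helps more after one therapy than after the other.

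The plan knows the usual tool for the second question: Hyp. 1.a adds an interaction term for experiential avoidance. None is stated for modafinil by initial arm.

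A posterior probability of benefit combines the size of an effect with the amount of data behind it. One arm above 0.80 and the other below is therefore weak evidence that the effects differ. The risk is a report that modafinil works only after ACT, or only after DC, when the effect is the same. The trial would also pass over the more precise overall estimate that its own re-randomisation provides.

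**Working it through.** **Inputs from the documents.** The trial enrols "N = 160 adults (18-60 years old) with cocaine use disorder". For the first stage, "Initial treatment response (abstinence) rates are expected to be" about 40%, and "we predict a difference in response rates, favoring ACT+CM over DC+CM by about 20" percentage points. Cell proportions have Beta(1,1) priors, missing urines count as positive, and the Go limit is 0.80. Table B.3.2.x states power 0.81 for 5 vs 6 (estimate 0.17) and 0.81 for 7 vs 8 (estimate 0.13). I take these rows to be the two within-arm modafinil contrasts; the numbered figure is not shown.

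**Assumptions.** Equal allocation at both randomisations, so 80 per initial arm.

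- Response 60%/40%: 80 × 0.40 = 32 and 80 × 0.60 = 48 non-responders, cells of 16 (ACT) and 24 (DC).
- Response 50%/30%: 40 and 56, cells of 20 and 28.
- Response 40%/40%: 48 and 48, cells of 24 and 24.

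Placebo abstinence is not readable and is varied.

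**Step 1: the stated power.** Under Beta(1,1), each rate has posterior Beta(1 + x, 1 + n − x). Per-arm power is the binomial probability of the results for which Pr(modafinil rate > placebo rate) exceeds 0.80. With the table's effects, these cells and placebo 10–40%, it is 0.54–0.74 for 5 vs 6 and 0.52–0.67 for 7 vs 8. At placebo 5% and 24 per cell, 5 vs 6 reaches about 0.81; 7 vs 8 stays at or below 0.76. The 0.81 is thus not generally reproduced. With the cell probabilities missing, that does not prove an error, so both routes are carried forward.

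**Step 2: exactly one arm crosses, on the stated power.** The arms contain different patients, so with per-arm powers a and b:

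P(exactly one) = a(1 − b) + b(1 − a) = 2 × 0.81 × 0.19 = 0.31.

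Both cross in 0.81² = 0.66 and neither in 0.19² = 0.04. The two 0.81 values belong to different average effects in the table, so this is the figure for a drug that works in both arms with that power in each.

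**Step 3: the same, on cells implied by N = 160.** True benefit of 15 points in both arms, exact enumeration:

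| Cells ACT/DC | Placebo 5% | 10% | 20% | 30% |
|---|---|---|---|---|
| 16/24 | 0.405 | 0.451 | 0.492 | 0.502 |
| 20/28 | 0.368 | 0.440 | 0.473 | 0.486 |
| 24/24 | 0.360 | 0.433 | 0.459 | 0.465 |

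At 16/24 and placebo 20%, a = 0.53 and b = 0.64, so 0.53 × 0.36 + 0.64 × 0.47 = 0.49. With placebo 10–40%, a 13-point benefit gives 0.47–0.51 and a 17-point benefit 0.39–0.49. With no effect in either arm and placebo 10–30%, exactly one crosses in 0.29–0.34, near 2 × 0.2 × 0.8 = 0.32.

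**Step 4: the role of cell size.** Identical observed rates of 37.5% versus 25% give a probability of benefit of 0.77 with 16 per cell (6 versus 4 abstinent) and 0.82 with 24 per cell (9 versus 6). So cell size alone can put two arms on opposite sides of 0.80. It is not what drives Step 3, however: at placebo 20%, equal cells of 20 give 0.489 against 0.492 for 16/24.

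**Step 5: the two missing quantities.** True benefit of 15 points in both arms, placebo 20%:

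- The pooled effect (cell-size-weighted mean of the two within-arm risk differences) crosses 0.80 in about 73–80% of trials, against about 53–68% for a single arm.
- The 95% interval for the difference of the two effects excludes zero in about 5%. Read at 0.80 in either direction, the same contrast would signal falsely in about 37–43%.
- With cells of 16 and 24, within-arm 95% intervals are about 0.56–0.60 and 0.47–0.50 wide. The interval for the difference is then about √(0.56² + 0.47²) = 0.73 to √(0.60² + 0.50²) = 0.78 wide. The pooled interval, with 40 per group, is about 0.37–0.40.

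**The case against.** Several points on the other side stand.

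- A reader might infer that the plan has no pooled modafinil effect at all. It does not go that far: the single augmentation indicator, as written, yields one common coefficient. What is missing is any hypothesis, power row or decision that uses it. With no product term stated, that coding also does not deliver the within-arm contrasts of Hyp. 2.
- Question 2 asks for estimates and precision as well as probabilities, so a careful report would show two intervals. That helps, but two intervals are still not an interval for their difference.
- No section says that one arm crossing 0.80 means arm-specific benefit; the 0.80 limit is for the Go decision. The discordance figures describe how often such a reading would be available, not a conclusion the plan commits to.
- A reader might infer that about half of trials would mislead. That overrides the stated 0.81, which gives 31%. Half is also close to the ceiling for two independent arms with equal power, so the figure largely reflects low per-arm power.
- Hyp. 2 and Aim 2 concern the best sequence of treatments, and the listed contrasts fit that aim. Whether a pooled contrast comes first is a matter of preference. Aim 2 is also labelled secondary.

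None of this supplies the missing contrast of effects, or defines how two probabilities are to be compared.

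**Conclusion.** The point holds in limited form. No contrast listed under Hyp. 2 or in Table B.3.2.x estimates the overall modafinil effect raised in the Project Summary, or the difference between the two modafinil effects that question 2 needs. Comparing two probabilities of benefit does not measure that difference.

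If the drug works in both arms, exactly one arm would cross 0.80 in about 3 trials in 10 on the plan's own power. On cells implied by N = 160 it would be roughly 35–50%. The second range rests on equal allocation, a 15-point benefit in both arms and placebo abstinence of 5–30%, none of which the readable text fixes. Both figures become false claims only if one-arm crossing is read as arm-specific benefit, which the plan neither states nor rules out. The documents do not support saying that the plan draws that conclusion, or that unequal numbers of non-responders cause most of the discordance.

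The change is worth making: it costs little, the data are the same, and the results feed a Go decision.

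**What to change.** 1. Add to Hyp. 2 a modafinil versus placebo contrast in all re-randomised non-responders, stratified by or standardised over initial arm. Reconcile it with the augmentation coding in the analytic strategy, and state the product term needed for the within-arm effects.
2. In question 2, replace the relative probabilities with the posterior of (modafinil minus placebo after ACT+CM) minus (modafinil minus placebo after DC+CM). Report it with a 95% interval and state that it is not judged at the 0.80 limit.
3. Keep the within-arm and sequence contrasts as planned, and state that one arm crossing 0.80 is not evidence of arm-specific benefit.

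The cost is SAP wording only, with no new patients or data. There are two drawbacks. The pooled effect is an average if modafinil truly works differently by arm. The difference will be imprecise, so it will often leave open whether the effects differ; the report should say so.

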exist. Posterior distributions can then be used as informative priors for continued monitoring in expansions of treatments and treatment strategies exhibiting initial promise.

Analytic strategy. Broadly, the analytic strategy will use generalized linear modeling. Continuous, dichotomous and time-to-event data will utilize linear, logistic, and proportional hazards regression respectively. Longitudinal analyses will employ generalized linear mixed models. All of these SAS (ver 9.3) procedures permit Bayesian analyses. Primary analyses will use intention-to-treat principles, with missing observations imputed as positive. Secondary analyses will implement joint modeling of observed outcomes and the missing data which is robust to ignorable missingness.^{81, 82} Sensitivity analyses will evaluate robustness of analytic conclusions to missing data. Non-ignorable missing data patterns will be addressed through pattern-mixture modeling methods.⁸¹ Prior distributions for comparison of proportions will use $\sim \text{Beta}(a = 1, b = 1)$ priors. Linear, logistic and Cox Proportional Hazards regression coefficient priors will take the form $\sim \text{N}(\text{mean} = 0, \text{var} = 1 \times 10^6)$ in the linear, log (odds) and log scales respectively. Level one error variances will be specified as $\sim \text{Inverse Gamma}(\text{shape} = 0.001, \text{scale} = 0.001)$; level two variances will use $\sim \text{Uniform}(0, 1000)$ distributions. Sensitivity analyses using optimistic and pessimistic, skeptical priors will evaluate prior assumptions.^{83, 84} Inverse probability weight will permit unbiased effect size estimates in the context of re-randomization. Finally, coding procedures will permit identification of each salient effect. Specifically, at the initial randomization ACT+CM and DC+CM will be coded as 1 and -1 respectively. For the re-randomization: 1) non-responders receiving continuation therapy will be coded 1 while all other participants will be coded 0; 2) non-responders receiving augmentation will be coded 1 versus 0 for all other participants.

Hypothesis testing.

Hyp. 1. Initial treatment with ACT+CM will produce higher response (abstinence) rates than initial treatment with DC+CM. Logistic regression will evaluate cocaine-abstinence rates at week 4 as a function of treatment assignment.

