small treatment effect favoring augmentation with modafinil, based on our previous trials.^{29, 31, 32, 43} Among initial responders, we previously observed that approximately 54% remain abstinent (46% "relapse") over an extended period of treatment, up to 12 weeks. Using this estimate for the control group (DC+CM), we predict a difference in response rates, favoring continued ACT+CM by about 15%, translating into a relapse rate of about 30%. Importantly, these effect size estimates are derived from data in which missing data is counted as non-abstinence, which mirrors the way we will be treating missing data for our primary analyses.

Finally, given the uncertainty inherent in pre-existing empirical evidence and even greater uncertainty for conditional probabilities of response, prudence dictated that robust trial planning rely upon probability distributions of plausible effects that take into account the uncertainty of our predictions of effect, rather than simple point-estimates. Adoption of distributional specification of effect sizes and their associated uncertainty required implementation of a Bayesian statistical approach.

Data Simulation Model. Using the above outcome estimates, we conducted a Monte Carlo simulation study to determine predicted power for the planned analyses, taking into account uncertainty in parameter estimates. **Figure B.3.2.x** depicts the trial design with probability point-estimates and 95% Credible Limits for each treatment cell, derived from logistic regression models with vague neutral priors, averaged across $K = 500$ simulations. *Simulated results for anticipated cell sizes are shown in italics.* **Table B.3.2.x** displays estimates of power to detect any benefit ($H_A: \theta > 0$) conferred by the treatment hypothesized as being superior. All primary hypotheses demonstrate a > 80% chance of detecting 0.90 probability of benefit for a sample of $N = 160$. Also shown in **Table B.3.2.x** are the point-estimates and 95% Credible Intervals of specified effects averaging over the $K = 500$ simulations.

Summary. Using data-driven effect sizes that take into account uncertainty, simulation results indicate that with a sample size $N=160$, we have roughly 80% power for all primary hypotheses. Further, we stipulate *a priori* that a > 80% chance of treatment conferring benefit (i.e. $Pr(\Pr \theta > 0 | \text{data}) > 0.80$)

[figure not shown]

Table B.3.2.x.

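### Hyp. 2: when a modafinil or placebo cell has no abstinent participant, the N(0, 10^6) logistic prior sets the size of the posterior probability, and the plan has no empty-cell rule

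*Combined protocol and SAP*

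**What the plan says.** In the combined protocol and SAP, Analysis Plan:

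- **Analytic strategy, priors.** "Linear, logistic and Cox Proportional Hazards regression coefficient priors will take the form" N(mean 0, variance 10^6), on the log-odds scale for logistic models (SD 1,000). A separate sentence covers simple proportions: "Prior distributions for comparison of proportions will use" Beta(1,1).
- **Hyp. 2.** Logistic regression of abstinence at the end of second treatment, with contrasts that include "modafinil versus placebo within each initial treatment".
- **Bayesian framework, question 2.** The effects of augmentation are wanted "for those initially receiving ACT+CM versus DC+CM; what are the best estimates of these effects and what is their precision".
- **Outcome and missing data.** The Power paragraph defines response as "two consecutive weeks of cocaine abstinence". Analytic strategy adds: "Primary analyses will use intention-to-treat principles, with missing observations imputed as positive".
- **Decision rule.** The Summary under Power treats a posterior probability of benefit above 0.80 as enough for Go.
- **Prior sensitivity.** "Sensitivity analyses using optimistic and pessimistic, skeptical priors will evaluate prior assumptions". No values are given, and the Go rule is not tied to these analyses.

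Nothing covers a cell with no abstinent participant. Hyp. 2 is listed as a secondary aim.

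**The concern.** With no success in the placebo cell, the likelihood keeps rising as the placebo log odds go to minus infinity (separation). Only the prior stops it. A prior SD of 1,000 on that scale puts nearly all its mass on success probabilities of practically 0 or 1, so it is far from neutral here. The posterior probability that the plan reports, and that the Go rule reads, then reflects the chosen variance. One success against none looks close to certain and ranks above better-supported results.

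An empty placebo cell is plausible. The participants are initial non-responders, the outcome needs two clean weeks, and missing samples count against abstinence. At stake are the reported probability and precision for the modafinil question and, in borderline tables, the Go reading.

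**Working it through.** **Inputs.** N = 160 (Study Site, Recruitment, Projected Enrollment), taken as 80 per initial arm. Initial response of about 40% with a difference of about 20 points (Power), taken as a range of 30% to 60%. Re-randomization is assumed 1:1. Cells are then 80 × (1 − 0.6)/2 = 16 to 80 × (1 − 0.3)/2 = 28. The placebo rate is in a figure not shown, so 5%, 10% and 20% are used.

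**The plan's own figure.** Table B.3.2.x gives power 0.81 at threshold 0.80 for contrasts 5 v 6 (effect 0.17) and 7 v 8 (effect 0.13). Its simulation used estimates "derived from logistic regression models with vague neutral priors". It cannot be firmly reproduced without the cell rates and sizes. As a rough check, a one-sided 0.20 test with a fixed effect of 0.17 gives 0.798 (n = 16, placebo 1%), 0.809 (n = 20, 3%), 0.819 (n = 24, 5%) and 0.793 (n = 28, 10%). That points to low placebo rates but does not prove them, because the plan averaged over uncertain effects.

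**Posterior at 1 v 0, logistic.** Integrating the two-cell posterior (intercept and modafinil slope, both N(0, 10^6)) gives 0.9992 for n = 16 to 28, and 0.9992 to 0.9996 over four codings. The answer follows the prior SD:

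| Prior SD | 1/24 v 0/24 | 3/24 v 1/24 |
|---|---|---|
| 2.5 | 0.60 | 0.78 |
| 5 | 0.80 | 0.85 |
| 10 | 0.91 | 0.875 |
| 100 | 0.992 | 0.883 |
| 1,000 | 0.999 | 0.883 |

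From SD 10 upward, 3 v 1 is settled by the data and 1 v 0 is not. The median log odds ratio at 1 v 0 is 477 (95% interval 22 to 1,584).

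**Risk difference, same model.** The placebo rate is forced to practically 0 and the modafinil rate is close to Beta(1, 23) at n = 24. The mean is 1/24 = 0.042, and the limits are 1 − 0.975^(1/23) = 0.001 and 1 − 0.025^(1/23) = 0.148.

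**Posterior at 1 v 0, Beta(1,1).** With n1 on modafinil and n0 on placebo, Pr(benefit) = 1 − n1(n1 + 1)/[(n1 + n0 + 1)(n1 + n0 + 2)].

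- 16 v 16: 1 − 272/1,122 = 0.758
- 24 v 24: 1 − 600/2,450 = 0.755
- 28 v 28: 1 − 812/3,306 = 0.754
- 14 v 18: 1 − 210/1,122 = 0.813

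At 3 v 1, Beta(1,1) gives 0.824 to 0.832, so the order reverses. At 1/16 v 0/16 the mean risk difference is 2/18 − 1/18 = 0.056 (95% interval −0.12 to 0.25).

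**Go rate per contrast with no true effect.** All tables were enumerated with equal cells. The chance of 1 v 0 is np(1 − p)^(2n − 1). At p = 0.05, n = 16 this is 0.8 × 0.95^31 = 0.163.

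| Abstinence | n | Logistic | Beta(1,1) | Chance of 1 v 0 |
|---|---|---|---|---|
| 5% | 16 | 26.3% | 10.0% | 16.3% |
| 5% | 24 | 25.6% | 14.3% | 10.8% |
| 5% | 28 | 25.1% | 15.8% | 8.3% |
| 10% | 16 | 24.2% | 17.9% | 6.1% |
| 10% | 24 | 23.2% | 17.9% | 1.7% |
| 10% | 28 | 22.9% | 18.0% | 0.9% |

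At 20% abstinence, 1 v 0 contributes at most 0.3 points.

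**Which arm is exposed.** If contrast 6 v 8 compares the two modafinil cells (an inference, as the figure is not shown), placebo abstinence after ACT+CM exceeds that after DC+CM by 0.13 + 0.16 − 0.17 = 0.12. With DC+CM placebo at 5%, an empty cell has probability 0.95^24 = 0.29. For ACT+CM at 17% and n = 16 it is 0.83^16 = 0.05.

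**The case against.** A reader might infer that the prior alone produces the Go at 1 v 0. The calculations do not support that. A Jeffreys prior has no separation problem and gives 0.82, which is also Go. Its false-Go rates at 5% abstinence are the same as the logistic ones (26.3%, 25.6%, 25.1%). Beta(1,1) itself passes at 1/14 v 0/18. Nor is the whole gap between logistic and Beta(1,1) an excess. A threshold of 0.80 has a nominal one-sided error near 20%; at n = 24 and 5%, logistic is 5.6 points above it and Beta(1,1) 5.7 below.

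A reader might also infer that the model gives no usable estimate at all. Table B.3.2.x appears to report differences in proportions, and the risk difference is finite. But its interval treats the placebo rate as known to be zero, so the precision is wrong.

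Other points carry some weight. Placebo non-responders still receive therapy and abstinence-based prize CM, so their rate may not be low. A skeptical prior would expose a 1 v 0 result (0.60 at SD 2.5), but its values are unstated and it does not govern Go. A model pooled over initial treatments without interaction avoids separation unless both placebo cells are empty, but it gives one common modafinil effect and not the planned contrast in each arm. With the interaction, the probability returns to 0.9995.

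**Conclusion.** The concern holds for tables with an empty cell. There, the planned prior gives a probability of benefit of about 0.999 for one success against none, ranks it above 3 v 1, and yields an unusable odds ratio and an interval that is too narrow. The effect on the Go reading is smaller: 1 v 0 sits close to the 0.80 threshold under reasonable priors. With no true effect and 5% abstinence, the false-Go rate is about 25% to 26%, against a nominal value near 20% and 10% to 16% under Beta(1,1).

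This rests on assumed cells of 16 to 28, 1:1 re-randomization and low placebo abstinence. The exposure is small at 10% unless cells are near 16, and negligible at 20%. Hyp. 2 is secondary, and the text does not say whether one contrast alone supports Go, so the rates are per contrast. It is worth settling before analysis but does not touch the primary hypothesis.

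**What to change.** State before analysis that, for any Hyp. 2 contrast with an empty or full cell, the probability of benefit, the risk difference, its 95% interval and the 0.80 Go reading come from Beta(1,1) cell posteriors. State also that the logistic probability and odds ratio are not used for that contrast. Keep the planned logistic model for all other tables. Because the trigger and the prior are fixed in advance, nothing is chosen after seeing the data. If the re-randomization probability is the same for every non-responder in an arm, the planned inverse probability weights are constant within a contrast and leave the cell proportions unchanged.

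At 5% abstinence the false-Go rate becomes 26.3 − 16.3 = 10.0% at n = 16, 25.6 − 10.8 = 14.8% at n = 24 and 25.1 − 8.3 = 16.8% at n = 28.

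The cost is one added rule and, with equal cells and low rates, power lost essentially only in 1 v 0 tables. For 22% v 5% at n = 16 the loss is 16 × 0.22 × 0.78^15 × 0.95^16 = 3.7 points. For 18% v 5% at n = 24 it is 24 × 0.18 × 0.82^23 × 0.95^24 = 1.3 points. It can be larger when cells are small and the effect is modest: 18% v 5% at n = 16 gives 16 × 0.18 × 0.82^15 × 0.95^16 = 6.5 points.

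Using Beta(1,1) for every Hyp. 2 table is not advised. At 34% v 17% (n = 16) it loses 5.1 points, only 0.05 of them from 1 v 0; at 18% v 5% (n = 24) it loses 6.0, only 1.3 from 1 v 0.
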